- Official Title: Effectiveness of Silver Diamine Fluoride in Arresting Early Approximal Carious Lesion Progression: A Pilot Study
- NCT Number: NCT02591147
- Document Date: May 1, 2022

Objective: The objective of this study is to evaluate the effectiveness of 38% Silver Diammine Fluoride (SDF) in arresting initial non-cavitated approximal carious lesion in adults aged 21-64 years utilizing three methods: pairwise comparison of individual radiographs, visual assessment of subtraction radiographs and histogram analysis of subtraction radiographs.

Design: This study is a randomized, triple-blinded, and placebo-controlled clinical trial (*ClinicalTrials.gov identifier-NCT02591147*). The study population consisted of adults aged 21-64 years old who are seeking care at the University of Iowa, College of Dentistry and Dental Clinics. Eligibility for the study includes having at least one initial non-cavitated approximal posterior carious lesion (Radiologic scores RA1, RA2, or RA3 using the International Caries Classification and Management System (ICCMS) scoring system) that was in contact with an adjacent non-restored tooth surface.

Methods: Consented subjects will be randomly assigned to one of the two study arms, either treatment (38% SDF solution) or placebo (water) designated as solutions "A" and "B". Participants will complete beverage intake and caries risk questionnaires at baseline and 12 months. The selected lesion will be followed at 6 and 12 months. A bitewing radiograph will be made at baseline utilizing a bite registration holder to insure close geometrical alignment of subsequent follow up radiographs. Lesion progression will be monitored radiographically through three methods: pairwise comparison of individual radiographs, visual assessment of subtraction radiographs and histogram analysis of subtraction radiographs.

Statistical Analysis Plan: The primary outcome of interest is whether there is caries progression based upon radiographic evaluation, evaluated at 12 months, for the two study arms. The analytic approach, which will utilize binary logistic regression modeling for correlated data, will consider the dependencies (correlations among data points) that typically arises with longitudinal data. For analyses targeting a specific time point, this is not a concern, because there is only a single measurement per individual, and standard binary logistic regression methods can be applied. A widely accepted method to deal with these types of dependencies is using generalized estimating equations (GEE). We will also consider mixed modeling approaches as part of these investigations as appropriate. Model selection will be guided by the use of Akaike's criterion and its modifications; particular considerations will be given to selection of the covariance structure addressing data dependencies, for which approaches have been developed in both the GEE and mixed modeling contexts. A primary goal in all analyses will be to formally compare the two treatment arms and, in doing so, to obtain estimates of effect sizes and associated variability for the planning of future trials. Throughout, the primary covariate of interest will be treatment arm; the effects of covariates including patient demographics, dietary intakes and behaviors, other aspects of caries risk assessment, and caries score (DMFT/DMFS) as a measure of disease burden and risk will also be assessed. All analyses will be carried out in accordance with intention-to-treat principles. The analyses just described will provide estimates of treatment effects and associated measures of variability to assist in planning a future definitive trial. In addition, attrition rates will be estimated, and 95% confidence intervals will be constructed for each time point and treatment arm. Because there is evidence that silver diamine fluoride is also a preventive agent, assessment of differences in incident caries between the two treatment groups is of particular interest as a secondary aim. We will consider measures reflecting the development of new lesions, considering issues of tooth eruption and loss between examinations (caries increment). The crude caries increment will be supplemented with net caries increment allowing for examiner reversals, and with the adjusted caries increment. Poisson models, or Poisson models augmented with an over dispersion parameter or an

extension to account for zero count inflation, have generally been found useful for examining the relationships between counts of affected teeth or surfaces, and can be applied to incident disease while accounting for correlated outcomes, including correlations among surfaces or subgroups of surfaces within an individual. Alternatives, such as the negative binomial model, are available if the Poisson is not appropriate. We note that linear regression approaches have sometimes been appropriately used to model caries increment. Candidate independent variables are as described above. Inter-and intra-rater reliability will be assessed for both radiographic and clinical measures of progression, using intraclass correlations for quantitative outcomes, and kappa statistics for categorical outcomes; weighted kappa will be used for ordinal categorical measures. Relationships between radiographic and clinical measures of progression will be assessed, using Spearman rank correlation when the two measures being compared are ordinal or quantitative. Binary outcomes (presence or absence of progression) will be assessed using McNemar's test (or the exact binomial test if appropriate); in this instance, evaluation of the level agreement of the two approaches will also be assessed using unweighted kappa. Descriptive statistics and graphics will further illustrate any identified relationships.

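### Does the plan need to state the histogram's scale, cut-point and role in the yes/no progression call?

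*Combined protocol and SAP*

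**What the plan says.** The histogram is named twice, in the Objective and in the Methods. The Methods state "Lesion progression will be monitored radiographically through three methods": pairwise comparison of radiographs, then "visual assessment of subtraction radiographs and histogram analysis of subtraction radiographs". The three are listed on an equal footing.

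The Statistical Analysis Plan does not mention the histogram. It defines the primary outcome thus: "The primary outcome of interest is whether there is caries progression based upon radiographic evaluation, evaluated at 12 months". The model is then given: "The analytic approach, which will utilize binary logistic regression modeling for correlated data", with GEE as the main tool for repeated measures. It adds: "We will also consider mixed modeling approaches as part of these investigations as appropriate". For a single time point the plan takes each person to contribute one measurement and uses ordinary logistic regression. Among the aims of all analyses is "to obtain estimates of effect sizes and associated variability for the planning of future trials".

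The closing part of the Statistical Analysis Plan foresees several types of progression measure. Reliability is to be assessed "using intraclass correlations for quantitative outcomes", with kappa or weighted kappa for categorical and ordinal ones. For the comparison of radiographic with clinical measures it says "Binary outcomes (presence or absence of progression) will be assessed" with McNemar's test. It does not say which type the histogram is.

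**The concern.** A histogram of a subtraction image would ordinarily be expected to yield a number, while the primary outcome is yes or no. If the histogram contributes to that outcome, some threshold must turn the number into a call, and the threshold is then part of the primary endpoint. If it does not contribute, a reader needs to know that it is a supporting measure, and what will be reported for it.

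Two things would be at stake. The progression rates and the effect size passed to the next trial would depend on an unstated cut. And if the cut, or the choice among methods, were settled only after the arms had been compared, the false-positive rate would rise above its nominal level.

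**Working it through.** **No figure to reproduce.** The documents give no sample size, significance level, expected progression rate or histogram threshold. All numerical inputs below are assumptions, used only to judge size.

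**Step 1: the texts side by side.**

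| Point | Objective and Methods | Statistical Analysis Plan |
|---|---|---|
| Methods of reading | three, with no order of priority | radiographic evaluation in general |
| Scale of the histogram | not given | not given; numeric, ordinal and binary measures are all provided for |
| Threshold for progression | none for any method | none for any method |
| Model | none | logistic, matching a yes/no outcome |

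No statement contradicts another. The gap also extends beyond the histogram: the pairwise and visual readings have no stated threshold either, and no method or combining rule is named for the single call.

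**Step 2: how far a cut-point could move the estimates.** Assume that a dichotomised histogram alone is the primary call. Let π be the true progression rate, d the movement of progressors and c the cut, both in SDs of reading noise. Only progressors move. Then

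observed rate = π·Φ(d − c) + (1 − π)·Φ(−c).

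Example: placebo π = 0.30, d = 2, c = 1 gives 0.30 × 0.841 + 0.70 × 0.159 = 0.363. Active π = 0.15 gives 0.15 × 0.841 + 0.85 × 0.159 = 0.261. The odds ratio is (0.261/0.739) / (0.363/0.637) = 0.62.

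| True rates, d | Result | c = 1 | 1.5 | 2 | 2.5 |
|---|---|---|---|---|---|
| 30% vs 15%, d = 2 | placebo rate | 36% | 25% | 17% | 10% |
| | OR | 0.62 | 0.56 | 0.52 | 0.51 |
| 30% vs 15%, d = 3 | placebo rate | 40% | 33% | 27% | 21% |
| | OR | 0.58 | 0.50 | 0.46 | 0.46 |
| 50% vs 25%, d = 2 | placebo rate | 50% | 38% | 26% | 16% |
| | OR | 0.49 | 0.47 | 0.47 | 0.48 |

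The observed rate moves a good deal. The odds ratio moves modestly, and hardly at all in the last case.

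**Step 3: set that against sampling error.** Assume 30 per arm. For the first column of the first case, the SE of the log odds ratio is √[1/(30 × 0.363) + 1/(30 × 0.637) + 1/(30 × 0.261) + 1/(30 × 0.739)] = 0.56. The 95% interval is 0.62 × exp(±1.96 × 0.56), about 0.2 to 1.9. The whole shift from 0.62 to 0.51 lies well inside it.

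**Step 4: false positives if the cut is picked afterwards.** In 40,000 simulated null trials (30% true progression in both arms, 20, 30 or 50 per arm), a single fixed cut gave 3.9–5.5%. Taking the best of cuts at 1, 1.5 and 2 SD gave 10.4–11.3% for d = 2 and 9.1–9.5% for d = 3.

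**Step 5: the wider question of combining methods.** If each of three methods called progression in an assumed 20% of lesions, independently, the rate would be 1 − 0.8³ = 48.8% if any method suffices, 3 × 0.2² × 0.8 + 0.2³ = 10.4% if two must agree, and 0.2³ = 0.8% if all three must. Readings of the same lesion are correlated, so the true spread would be narrower.

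**The case for a change.** The strongest case for acting is that estimation is the purpose of this pilot, so a definition that moves observed placebo progression from 36% to 10% affects exactly what it is meant to deliver. That holds even where the odds ratio is stable: in the 50% against 25% case the placebo rate still falls from 50% to 16%. The remedy would be a few sentences and no new data. The allowance for mixed models does not fill the gap, because in context it concerns correlated observations, not a numeric outcome. The rules by data type cover reliability and agreement only, not the comparison of arms.

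Much of this stands. The omission is confirmed, no redaction explains it, and the sensitivity of observed rates is real under the assumed model. Three parts do not carry through.

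- Every figure in Steps 2 to 4 supposes that a dichotomised histogram alone is the primary call. The plan does not say so, and if the histogram is supportive those figures do not describe the primary outcome.
- The error-rate argument supposes a choice made with the arms in view. Nothing plans this. The Design is triple-blinded and the Methods label the solutions A and B, which gives some protection, though it is not a written rule.
- Taking a cut from the noise in planned repeat readings is doubtful. The reliability work addresses rater variation, whereas differences in alignment and exposure between visits are a separate source of noise that re-reading the same images need not capture.

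**Conclusion.** No change to the plan follows. This is a gap in definition that analysts can be expected to fill: decide, while the arms are still coded, what constitutes progression at 12 months, treat the remaining readings as supporting, and describe a numeric histogram result by an ordinary between-arm difference with its interval. Nothing in the plan obstructs that, no stated rule gives a wrong answer, and the primary yes/no outcome has a suitable model.

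On the assumed inputs, the cut-point could shift the odds ratio by about 0.1 (0.62 to 0.51 or 0.58 to 0.46) or by almost nothing (0.47 to 0.49). At 30 per arm, sampling error exceeds that several times over. The larger movement is in observed progression rates, and the 9–11% false-positive figure arises only if the cut is chosen after the arms are seen. The histogram is also too narrow a target, since the same silence covers all three methods.

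The conclusion rests on the pilot aim and on the definition being settled before the arms are compared. The second is a reasonable expectation under the blinding described, but the documents do not state it.

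### Baseline lesion stage (RA1–RA3) is scored but not fixed in the 12-month arm comparison; adjusting for it is a cheap way to sharpen the marginal risk difference if stage predicts progression

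*Combined protocol and SAP*

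**What the plan says.** The Design paragraph admits lesions by stage: "Radiologic scores RA1, RA2, or RA3 using the International Caries Classification and Management System (ICCMS) scoring system". The Methods paragraph follows one lesion per participant: "The selected lesion will be followed at 6 and 12 months". Taking the selected lesion to be the qualifying one, every study lesion has a stage recorded before treatment.

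The Statistical Analysis Plan defines its main endpoint as follows: "The primary outcome of interest is whether there is caries progression based upon radiographic evaluation, evaluated at 12 months, for the two study arms". For a single time point the plan notes that "there is only a single measurement per individual, and standard binary logistic regression methods can be applied". Treatment arm is the covariate of main interest. Beyond arm, the plan will assess "the effects of covariates including patient demographics, dietary intakes and behaviors, other aspects of caries risk assessment, and caries score (DMFT/DMFS"), the last as a marker of burden and risk in the whole mouth. On choosing among models it says "Model selection will be guided by the use of Akaike's criterion and its modifications", with emphasis on the covariance structure. A stated goal is to "obtain estimates of effect sizes and associated variability for the planning of future trials".

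RA stage appears nowhere in the Statistical Analysis Plan. No baseline term is declared as always included, and no stratification of the randomisation by stage is described.

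**The concern.** The outcome is progression of one lesion, yet every covariate named describes the patient or the whole mouth. The obvious lesion-level candidate is already scored. As written, it could be in the model, out of it, or chosen after the data are seen.

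Two things are at stake. The first is precision: if lesions at different stages progress at different rates, the unadjusted arm difference carries avoidable noise from chance differences in stage mix. The second is clarity of what is handed to the planners of the next trial. An odds ratio adjusted for stage and an unadjusted one estimate different quantities, and nothing says which will be reported.

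**Working it through.** **Inputs.** The documents give no sample size, stage mix, progression rates or effect size, so there is no figure to reproduce and everything here is assumed:
- 1:1 allocation;
- RA1, RA2 and RA3 in equal thirds;
- within-stage odds ratio 0.30;
- placebo progression by stage of 30/37/44% (weak), 21/35/52% (mild), 15/35/60% (middle) or 10/35/73% (strong).

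**Formulas.** Let c and t be the stage-specific progression risks on placebo and treatment, and pc and pt their averages. With n per arm:
- unadjusted: n × variance of the risk difference = pc(1−pc) + pt(1−pt);
- adjusted for stage and standardised: n × variance = E[c(1−c)] + E[t(1−t)] + Var(t−c)/2.

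The second formula is for full adjustment. A single ordinal term comes close to it here because the assumed gradients are nearly linear on the logit scale.

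**Middle case.**
1. Treated odds are 0.30 × placebo odds, so t = 5.03/13.91/31.03%. Then pc = 0.3667 and pt = 0.1666.
2. Unadjusted: 0.2322 + 0.1388 = 0.3710.
3. Adjusted: 0.1983 + 0.1272 + 0.0030 = 0.3285.
4. Variance ratio 0.3285/0.3710 = 0.885; SD ratio √0.885 = 0.941; equivalent sample size 1/0.885 = 1.13.
5. At an assumed 40 per arm, the SE is √(0.3710/40) = 9.6 points unadjusted and √(0.3285/40) = 9.1 points adjusted.

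**The odds ratio, same case.** The marginal odds ratio is (0.1666/0.8334)/(0.3667/0.6333) = 0.345, against 0.30 within stage. The SE of the log odds ratio, times √n, is √(1/0.2322 + 1/0.1388) = 3.39 unadjusted and 3.64 from the information matrix of the model with arm and ordinal stage, so it rises by about 7%. The test statistic still gains, because the log odds ratio moves further from zero: (ln 0.30/ln 0.345)/1.073 = 1.055.

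**All cases, large sample.**

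| Gradient | SD of risk difference | Worth in participants | SE of log odds ratio | Test statistic |
|---|---|---|---|---|
| Weak | −0.5% | +1% | +0.6% | +0.5% |
| Mild | −3% | +6% | +3% | +2.5% |
| Middle | −6% | +13% | +7% | +5.5% |
| Strong | −12.5% | +31% | +17% | +12% |

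With a 60/30/10% stage mix, the SD falls by only 0.4, 1.9, 4.6 or 9.8%.

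**Small samples.** These come from simulation with one ordinal term, 4,000 trials per setting.
- No gradient: SD ratio 1.016, 1.007, 1.007 and 1.004 at 20, 30, 40 and 60 per arm, a small loss.
- Mild gradient: 0.987, 0.980, 0.984 and 0.978. At 20 per arm, power is unchanged (26.8% unadjusted, 27.0% adjusted).
- No treatment effect (middle and strong gradients): rejection rates 3.7–5.4% unadjusted and 3.9–5.1% adjusted at a nominal 5%.

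Two stage indicators cost more. In a separate simulation with 15 per arm and a risk ratio of 0.5, the variance ratio was 1.10 with no gradient and 1.03 for placebo rates of 20/30/40%.

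**The case against.** The strongest objection is that the premise is not in the documents. Nothing says that RA stage predicts 12-month progression. The outcome compares each lesion with its own baseline image, so stage may already be partly accounted for. This stands: the plausible range runs from a slight loss to a useful gain, and the documents cannot place the trial within it.

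Next, the plan names logistic, GEE and mixed models and never a risk difference, so the gain lies in a quantity the plan does not yet report. This also stands, and it is why a covariate alone is not enough. A reader might infer that adding stage will tighten the planned odds ratio. It will not; that SE rises.

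Third, the gain is least certain in a small pilot, and separate stage indicators can fail. In simulation at 20 per arm, some stage had all or no events in 17% (mild), 29% (middle) and 44% (strong) of trials. This is an argument for the single ordinal term. That term does not depend on an exactly linear gradient: with placebo rates of 20/20/70%, the simulated SD ratio was still 0.90–0.91.

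Finally, the covariate list is open, so stage might be used anyway. That is correct, and it rules out the tempting reading that the plan excludes stage. What remains is that its use is not fixed in advance.

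**Conclusion.** The point holds as an optional, low-cost improvement. Stage is available, unnamed and not fixed in the 12-month comparison. If it is prognostic, a standardised risk difference gains about 0.5 to 12.5% in SD, equivalent to about 1 to 31% more participants. The upper end needs a placebo gradient from 10% to 73%. These sizes rest wholly on the assumed rates, stage mix and odds ratio.

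A reader might go further and infer that the unadjusted analysis is biased or invalid. The documents do not support that: participants are randomised, and the unadjusted comparison remains valid. Nor do they support any claim that stage is known to be prognostic in this population.

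**What to change.** In the Statistical Analysis Plan, before the arm codes are broken:
- Pre-specify baseline RA stage as a single ordinal (one degree of freedom) term alongside arm in the 12-month logistic model, and include the same term in the longitudinal GEE or mixed model.
- From the 12-month model only, report standardised progression risks per arm and their difference, with a delta-method or bootstrap confidence interval. Limiting this to the 12-month model avoids averaging over random effects.
- Show the unadjusted risks and difference beside them.
- Name the marginal estimate as the one used for planning, and report the conditional odds ratio separately.

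The cost is a few sentences and no new data. The downsides are:
- one degree of freedom;
- about nil gain if stage is weakly prognostic, or with a mild gradient at about 20 per arm;
- up to about 2% larger SD if stage is not prognostic;
- a conditional odds ratio with a larger SE, which must not be confused with the marginal estimate.
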